### 7.9.8 Stomatitis and Mucositis

Preventive measures may include a comprehensive oral examination to identify and treat any potential risk for complications before study treatment is initiated. Appropriate correction of local factors should be instituted as indicated, such as modification of ill-fitting dentures and appropriate care of gingivitis.

During treatment with cabozantinib, good oral hygiene and standard local treatments such as non-traumatic and non-irritating cleansing, and oral rinses (e.g. with a weak solution of salt and baking soda) should be maintained. Lips should be kept moisturized with lip balm. The use of lipstick, lip-gloss, and Vaseline should be avoided.

Local treatment should be instituted at the earliest onset of symptoms. Obtain bacterial/viral culture if oral infection is suspected and treat infection as clinically indicated.

### 7.9.9 Skin and Subcutaneous Tissue Disorders

Wound healing and surgery: Cabozantinib has the potential to cause wound healing complications and wound dehiscence which may even occur long after a wound has been considered healed. Therefore, surgical and traumatic wounds must not only be completely healed prior to starting cabozantinib treatment but must also be monitored for wound dehiscence, wound infection and

other signs of impaired wound healing while the subject is being treated with cabozantinib. If dehiscence occurs, cabozantinib treatment should not be restarted until complete healing has taken place.

Treatment with cabozantinib should be stopped at least 28 days prior to scheduled surgery. The decision to resume treatment with cabozantinib after surgery should be based on clinical judgment of adequate wound healing.

Palmar-plantar erythrodysesthesia syndrome (PPES) (PPES; also known as hand-foot syndrome), skin rash (including blister, erythematous rash, macular rash, skin exfoliation, dermatitis acneiform, and papular rash), pruritus, dry skin, erythema, pigmentary changes, and alopecia have been reported with cabozantinib. All subjects on study should be advised on prophylactic measures including the use of emollients, removal of calluses, avoidance of exposure of hands and feet to hot water leading to vasodilatation, protection of pressure-sensitive areas of hands and feet, and use of cotton gloves and socks to prevent injury and keep the palms and soles dry.

Early manifestations include tingling, numbness, mild hyperkeratosis, and symmetrical red and swollen areas on the palms and soles. The lateral sides of the fingers or periungual zones may also be affected. Adequate interventions are required to prevent worsening of skin symptoms such as blisters, desquamations, ulcerations, or necrosis of affected areas. Analgesics may be required for pain control. Aggressive management of symptoms is recommended, including early dermatology referral. Treatment recommendations in response to PPES are summarized in the table below.

**Table 7.6: Management of Hand-Foot Syndrome (PPES) Associated with Cabozantinib**

Event	Management
Grade 1	Cabozantinib treatment may be continued at the current dose if PPES is clinically insignificant and tolerable. Otherwise, cabozantinib should be reduced to the next lower dose level. a Start urea 20% cream twice daily AND clobetasol 0.05% cream once daily. Reassess at least weekly; if PPE worsens at any time or does not improve after 2 weeks, proceed to the intervention guidelines for Grade 2.
Grade 2	Cabozantinib treatment may be continued if PPES is tolerated. Cabozantinib should be dose reduced or interrupted if PPES is intolerable. Continue urea 20% cream twice daily AND high potency steroid cream (e.g., clobetasol 0.05%) once daily and add analgesics (e.g., NSAIDs/gamma-aminobutyric acid agonists) for pain control if needed. Reassess at least weekly; if PPE worsens or affects self-care, proceed to the intervention guidelines for Grade 3.
Grade 3	Interrupt cabozantinib treatment until severity decreases to Grade 1 or 0. Continue treatment of skin reaction with high potency steroid cream (e.g., clobetasol 0.05%) twice daily AND analgesics. Resume cabozantinib at a reduced dose if PPES recovers to Grade ≤ 1. Discontinue subject from cabozantinib if PPES does not improve within 6 weeks.
b Permitted dose levels are defined by individual protocols.	

### 7.9.10 Osteonecrosis

Osteonecrosis has been reported in subjects treated with cabozantinib. Additional risk factors include use of bisphosphonates and denosumab, chemotherapy and anti-angiogenic drugs, use of corticosteroids, local radiotherapy, and dental or orofacial surgery procedures.

Osteonecrosis of the jaw (ONJ) can manifest as jaw pain, osteomyelitis, osteitis, bone erosion, tooth or periodontal infection, toothache, gingival ulceration, or gingival erosion. Persistent pain or slow

healing of the mouth or jaw after dental surgery may also be manifestations of osteonecrosis. Advise subjects regarding oral hygiene practice and to quickly report symptoms to investigator. Caution should be used in subjects receiving bisphosphonates.

Invasive dental procedures should be avoided. In cases where dental procedures are unavoidable, treatment with cabozantinib should be interrupted for at least 4 weeks prior to the procedure and resumed after complete wound healing has occurred. Bone healing may often require a protracted time.

If ONJ occurs, cabozantinib treatment should be held and should not be restarted until the condition has sufficiently healed and the Sponsor has approved the re-initiation of therapy.

#### **7.9.11 Proteinuria**

Proteinuria has been reported with cabozantinib. Proteinuria should be monitored by measuring UPCR.

The table below provides treatment guidelines for proteinuria deemed related to cabozantinib. Cabozantinib should be discontinued in subjects who develop nephrotic syndrome (proteinuria >3.5 grams per day in combination with low blood protein levels, high cholesterol levels, high triglyceride levels, and edema).

**Table 7.7: Management of Proteinuria Associated with Cabozantinib**

Event	Management
UPCR $\leq 1$ mg/mg ( $\leq 113.1$ mg/mmol)	
 
No change in cabozantinib treatment or monitoring.
 

UPCR $> 1$ and $< 3.5$ mg/mg ( $> 113.1$ and $< 395.9$ mg/mmol)	
 
Consider confirming with a 24-h protein assessment within 7 days.
 
No change in cabozantinib treatment required if UPCR <math>\leq 2</math> mg/mg or urine protein <math>\leq 2</math> g/24 h on 24-h urine collection.
 
Dose reduce or interrupt cabozantinib treatment if UPCR <math>> 2</math> mg/mg on repeat UPCR testing or urine protein <math>> 2</math> g/24 h on 24-h urine collection. Continue cabozantinib on a reduced dose if UPCR decreases to <math>< 2</math> mg/mg. Consider interrupting cabozantinib treatment if UPCR remains <math>> 2</math> mg/mg despite a dose reduction until UPCR decreases to <math>< 2</math> mg/mg. Restart cabozantinib treatment at a reduced dose after a dose interruption.
 
Repeat UPCR within 7 days and once per week. If UPCR <math>< 1</math> mg/mg on 2 consecutive readings, UPCR monitoring can revert to protocol-specific times. (Second reading is confirmatory and can be done within 1 week of first reading.) If UPCR remains <math>> 1</math> mg/mg and <math>< 2</math> mg/mg for 1 month or is determined to be stable (<math>< 20\%</math> change) for 1 month, check urine protein/creatinine per protocol or as clinically indicated.
 

UPCR $\geq$ 3.5 mg/mg ( $\geq$ 395.9 mg/mmol)	
 
Interrupt cabozantinib treatment pending repeat UPCR within 7 days and/or 24-h urine protein.
 
If <math>\geq</math> 3.5 mg/mg on repeat UPCR, continue to hold cabozantinib treatment and check UPCR every 7 days. If UPCR decreases to <math><</math> 2 mg/mg, restart cabozantinib treatment at a reduced dose and monitoring of urine protein/creatinine should continue weekly until the UPCR decreases to <math><</math> 1 mg/mg. If UPCR remains <math>></math> 1 mg/mg and <math><</math> 2 mg/mg for 1 month or is determined to be stable (<math><</math> 20% change) for 1 month, check urine protein/creatinine per protocol or as clinically indicated.
 

Nephrotic syndrome	
 
Discontinue cabozantinib treatment.
 

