 cfDNA, circulating immune activity, lipase can be collected within 30 days prior to C1D1 or pre-dose C1D1

 When plasma DNA is collected, it should be collected as close to biopsy date as possible, including same day. In the event it is collected on the same day, the specimen should be acquired *prior* to the biopsy procedure.

 Every 12 weeks (± 5 days) until disease progression. For EOT, does not have to be repeated if done within 6 weeks of visit.

 Assess continuously until disease progression

 Every 12 weeks beginning with C4D1 (e.g. C4, C7, C10, etc).

 Collect only on C4D1

 Pre-treatment biopsy can be waived provided that adequate archival material for molecular analyses available from biopsy performed within 3 months of enrollment

 On-treatment biopsy during cycle 1 after 3 weeks of therapy. Biopsy must be performed between day 21 and day 24 on therapy (inclusive). *NB: cabozantinib must be held 5 days before and 5 days after biopsy*

Cycle = 28 days	Screening	Cycle 1			Cycle 2	Cycle 3	Cycle 4 +	End of Treatment	Survival Follow-Up
	Day -30 to -1	Day 1	Day 14	Day 21 (+ 3 days)	Day 1 (± 3 days)	Day 1 (± 3 days)	Day 1 (± 3 days)	Post-Treatment	
Concomitant medications 	X	X			X	X	X	X	
Adverse events 	X	X	X		X	X	X	X	
Health Care Resources 	X	X			X	X	X	X	
Cabozantinib dosing 		X			X	X	X		
Dispense/return of oral study drug and compliance accounting		X			X	X	X	X	
Additional cancer treatment, survival status								X	Subjects will be followed every 12 weeks for 2 years after completion of the study or until death, whichever occurs first

 Document those taken from 30 days prior to treatment through 30 days after the decision to discontinue study treatment

 Document new or worsening events from time of informed consent through 30 days after the last dose of study treatment (related SAEs at any time). Adverse events information will be collected at study visits and may also be collected at any time over the phone or by spontaneous subject report. At study visits where any study treatment is administered, adverse events will be documented pre- and post-dose. Certain AEs and all SAEs that are ongoing 30 days after last dose of study treatment are to be followed until resolution or determination by the investigator that the event is table or irreversible.

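### Table 7.7 applies both a no-change and a reduce-or-interrupt rule when UPCR and an optional 24-hour protein fall on opposite sides of 2, and its stable clause states no UPCR range

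*Combined protocol and SAP*

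**What the plan says.** All of the dosing text is in Section 7.9.11, Table 7.7.

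**Row for UPCR above 1 and below 3.5 mg/mg**
- The 24-hour collection is optional: "Consider confirming with a 24-h protein assessment within 7 days". The repeat UPCR within 7 days, and weekly after that, is an instruction.
- The bullet opening "No change in cabozantinib treatment required if UPCR" is met by UPCR at or below 2 mg/mg *or* urine protein at or below 2 g in 24 hours.
- The bullet opening "Dose reduce or interrupt cabozantinib treatment if UPCR" is met by UPCR above 2 "mg/mg on repeat UPCR testing or urine protein" above 2 g in 24 hours.
- Weekly checks may end if UPCR stays above 1 and below 2 "mg/mg for 1 month or is determined to be stable" (less than 20% change) over a month. Checks then follow the protocol schedule or clinical need.

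**Row for UPCR at or above 3.5 mg/mg**
- If the repeat confirms the value, sites are to "continue to hold cabozantinib treatment and check UPCR every 7 days". Restart at a reduced dose follows a fall below 2, with weekly monitoring until UPCR is below 1.
- The row ends with the same sentence on relaxing the checks, including the limb "or is determined to be stable".

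**Protocol schedule.** In Section 6.1, UPCR is measured at screening and then, by footnote 8, "Every 12 weeks beginning with C4D1 (e.g. C4, C7, C10, etc".

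**The concern.** A dosing table should return one instruction for one set of results. Here the two bullets are built from opposite limbs, yet both are joined by *or*, so they are not complements of each other. A man with one result on each side of 2 qualifies under both, and neither Table 7.7 nor the text of Section 7.9.11 says which measurement governs. About eight sites are expected (Section 4.7). Two of them could follow the table faithfully and act differently on the same results.

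The monitoring clause has a separate gap. Its first limb carries a range (above 1 and below 2), but its stable limb carries none. A steady UPCR above 2 can therefore leave weekly checks. Yet the same row asks sites to consider interruption while UPCR stays above 2 despite a dose reduction, until it falls below 2, and that depends on continued measurement.

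**Working it through.** There is no sample-size, power or alpha figure to reproduce. The check is one of logic and of the calendar.

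**1. The two bullets as conditions.** Let U be UPCR (mg/mg) and P be 24-hour protein (g).
- No change: U ≤ 2 or P ≤ 2.
- Reduce or interrupt: repeat U > 2 or P > 2.

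The complement of (U ≤ 2 or P ≤ 2) is (U > 2 *and* P > 2). The second bullet says *or*, so the two overlap wherever U and P lie on opposite sides of 2.

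**2. Worked pairs (illustrative values)**

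| UPCR | Repeated? | 24-h protein | No change | Reduce or interrupt |
|---|---|---|---|---|
| 1.8 | no | 1.5 g | yes | no |
| 1.8 | no | 2.4 g | **yes** | **yes** |
| 2.5 | no | 1.6 g | yes | no |
| 2.5 | yes, 2.5 | 1.6 g | **yes** | **yes** |
| 2.5 | yes, 2.5 | 2.6 g | no | yes |
| 2.5 | yes, 2.5 | not done | no | yes |

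With UPCR at or below 2 and 24-hour protein above 2 g, the conflict arises at once. With UPCR above 2 and 24-hour protein at or below 2 g, it arises only when the repeat UPCR is also above 2.

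**3. Grid.** Repeat UPCR and 24-hour protein each run from 1.1 to 3.4 in steps of 0.1, giving 24 × 24 = 576 pairs. Ten values are at or below 2 and 14 are above, so 2 × 10 × 14 = 280 pairs are discordant. All 280 meet both bullets, and none of the 296 concordant pairs does. If the UPCR has not been repeated, only the 140 pairs with UPCR ≤ 2 and protein > 2 g meet both. These counts describe the rule and are not patient frequencies.

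**4. Source of the overlap.** As a logic test only, changing *or* to *and* in either bullet leaves 0 overlapping pairs. The two changes give opposite answers for the discordant pairs, so choosing between them is a clinical decision.

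**5. Why the tests can disagree.** 24-hour protein (g) = UPCR × daily creatinine excretion E (g/day), so the cut-offs coincide only at E = 1. The documents give no E. Under assumed values the conflicting UPCR band lies between 2 and 2/E:
- E = 0.8: 2.0 to 2.5
- E = 1.2: 1.67 to 2.0
- E = 1.5: 1.33 to 2.0

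The row is 2.5 mg/mg wide, so these bands are 0.5/2.5 = 20%, 0.33/2.5 = 13% and 0.67/2.5 = 27% of it. They are shares of the row, not of patients.

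**6. Stable clause.** Take change relative to the first value; the table does not define the reference. An illustrative weekly series of 2.6, 2.7, 2.5, 2.6, 2.6 has a largest change of 0.1/2.6 = 3.8% and qualifies, although every value is above 2. A series of 4.0, 4.2, 3.9, 4.1, 4.0 in the higher row has a largest change of 0.2/4.0 = 5% and also meets the words. The protocol interval is 3 cycles × 28 days = 84 days, against 7 days for weekly checks.

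**The case against.** **The 24-hour test is optional and confirmatory.** *Or* may simply mean whichever confirmation was done, and without a collection there is no conflict. That limits the reach. But the row invites the collection, and both bullets give its result a limb of its own, so the conflict remains when both results exist.

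**The wording is permissive.** Saying that no change is required does not forbid a reduction. Section 7.9.11 calls the table guidelines, and Section 7.8.1 already leaves reductions and interruptions to investigator discretion. This is fair, and it keeps the point minor. It does not explain why one pair of results should satisfy both bullets.

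**Stronger readings.** A reader might infer that any disagreement between the tests triggers both rules. The documents do not support that, because a first UPCR above 2 with 24-hour protein at or below 2 g meets only the no-change bullet until it is repeated.

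A reader might also infer that a man held at a steady 4 mg/mg is moved to 12-weekly checks. That is at most a permitted extreme:
- The clause also allows checks by clinical need.
- It follows the restart sentence, so it may be meant only for men back on drug.
- The held man has his own 7-day instruction.
- Section 7.8.1 normally ends treatment after more than 6 weeks of interruption for a related event, unless benefit is unequivocal. With a month taken as 28 to 31 days, a month of stability leaves 42 − 31 = 11 to 42 − 28 = 14 days before that limit.

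What stands is that the row does not state the treatment status to which the clause applies.

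**Conclusion.** The point holds as a narrow internal contradiction plus an undefined scope. In the row above 1 and below 3.5, a UPCR at or below 2 with 24-hour protein above 2 g, or a repeat UPCR above 2 with 24-hour protein at or below 2 g, meets both dosing bullets with no tie-break. The stable limb lacks a UPCR range in both rows, and in the higher row it competes with the 7-day instruction because its treatment status is not stated.

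The number of men affected cannot be derived from the documents. Section 7.9.2 places proteinuria among the less frequent events, outside the list of those seen in at least 20%. If that means below 20% (an inference), fewer than 0.20 × 30 = 6 men would be expected to have it. Only those with a 24-hour collection that disagrees around 2 would meet the dosing conflict. No discordance rate should be read from the grid or from the bands in the working. The point bears on no endpoint analysis in Section 12. It is minor, but it concerns dosing and is easily corrected.

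**What to change.** Two edits to Table 7.7:

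1. Reword the two dosing bullets in the row above 1 and below 3.5 so that they cannot both be true for one pair of results, for example by stating which measurement governs when UPCR and 24-hour protein disagree.
2. In both rows, state the UPCR range to which the stable limb applies, and whether it applies on drug, while held, or both.

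The sponsor and investigator must choose the rule and the range; none is proposed here. The cost is a few words in one table by amendment, with no new tests or visits and no change to the analysis.

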### 7.9.12 Nervous System Disorders

Cabozantinib appears to represent minimal risk of adverse neurological effects based on nonclinical Good Laboratory Practice (GLP)-compliant toxicology studies. Dysphonia, dysgeusia, headache, dizziness, confusional state, convulsion, depression, memory impairment, hypoesthesia, peripheral neuropathy, insomnia, ataxia, and encephalopathy have been observed in clinical studies with cabozantinib. The development of any new or progressive, unexplained neurological symptoms should be assessed for underlying causes.

RPLS has been reported. RPLS should be considered in any subject presenting with seizures, headache, visual disturbances, confusion or altered mental function. Cabozantinib treatment should be discontinued in subjects with RPLS.

### 7.9.13 Hepatocellular Toxicity

Elevation of aminotransferases (ALT and AST): Evaluation of subjects with elevated transaminases or bilirubin should be individualized and guided by the presence of specific risk factors such as liver conditions (e.g. liver cirrhosis, metastases to the liver, thrombosis of portal or hepatic vein, hepatocellular carcinoma, hepatitis), concomitant hepatotoxic medication, alcohol consumption, and cancer related causes.

Cabozantinib should be interrupted for related CTCAE Grade 3 or higher hepatic injury (transaminase increase to  $> 5 \times$  ULN) and when transaminase increases are accompanied by progressive elevations of total bilirubin, and/or elevations of coagulation tests (e.g. International Normalized Ratio [INR]). More frequent monitoring of transaminases should be considered and cabozantinib should be interrupted until the etiology of the abnormalities is determined and these abnormalities are corrected or stabilize at clinically acceptable levels. Cabozantinib should be discontinued if hepatic dysfunction is not reversed despite interruption of study treatment. Elevations of aminotransferases when hepatic metastases are present may not require dose modifications if there are no progressive changes in the aminotransferases (less than a doubling) and if there are no progressive elevations in serum bilirubin concentration or coagulation factors. Elevations  $>3 \times$  ULN of ALT or AST concurrent with  $>2 \times$  ULN total bilirubin without other explanation (such as initial findings of cholestasis and obstructive disease, viral hepatitis, pre-existing or acute liver disease, or another drug capable of causing the observed injury) can indicate drug-induced liver injury (DILI). Study drug should be permanently discontinued in cases determined to be DILI according to Hy's Law review.

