### **7.8.2 Cabozantinib Dose Reinstitution and Reescalation**

If the subject recovers from his or her toxicities to CTCAE v.4.0 Grade  $\leq 1$  or to the baseline value (or lower) and the toxicity was unrelated to study treatment, then study treatment may be restarted with no change in dose.

If the subject recovers from his or her toxicities to Grade  $\leq 1$  or to the baseline value (or lower) the toxicity was deemed possibly related to study treatment, then study treatment may be restarted at a reduced dose (see Table 7.2 for the schedule of dose reductions).

Subjects receiving a daily dose of 20 mg may be restarted at the same dose if deemed safe at the discretion of the investigator. Subjects unable to tolerate a daily dose of 20 mg should discontinue study treatment.

Re-escalation to the previous dose, (but not higher than 40 mg/day) may be allowed at the discretion of the investigator for AEs which have resolved or recovered to Grade 1 (or baseline value) and deemed tolerable and easily managed by optimized supportive treatment. Dose re escalation is not allowed for a drug-related dose reduction triggered by Grade 4 hematologic toxicities or by Grade 4 AEs affecting major organs (e.g. central nervous system, cardiac, hepatic, renal).

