**Table 7.8: Management of Hepatocellular Toxicity Associated with Cabozantinib**

Event – Elevation of ALT, AST, or Total Bilirubin (CTCAE v4)	Management
Grade 1  ALT or AST > ULN – 3.0 x ULN Bilirubin > ULN – 1.5 x ULN	
 
• Dose adjustment is usually not required.
 
• Consider discontinuing concomitant hepatotoxic medications and add supportive care as indicated.
 

Grade 2 a,b  ALT or AST > 3.0 – 5.0 x ULN Bilirubin > 1.5 – 3.0 x ULN	
 
• Interrupt cabozantinib if lasting longer than 1 week and consider more frequent monitoring of ALT, AST, and bilirubin.
 
• Restart cabozantinib after lab abnormalities have resolved to at least CTCAE Grade ≤ 1 or baseline.
 

Grade 3 a,b  ALT or AST > 5.0 – 20.0 x ULN Bilirubin > 3.0 – 10.0 x ULN	
 
• Interrupt cabozantinib and consider more frequent monitoring of ALT, AST, and bilirubin.
 
• Restart cabozantinib at a reduced dose after lab abnormalities have resolved to at least CTCAE Grade ≤ 1 or baseline.
 
• Discontinue if lab abnormalities cannot be reversed despite interruption of study treatment.
 

Grade 4 b  ALT or AST > 20.0 x ULN Bilirubin > 10 x ULN	
Subjects should have cabozantinib interrupted immediately. Discontinue cabozantinib unless the following criteria are met:
 
 
• Subject is deriving clear clinical benefit as determined by the Investigator, and approved by the Principal Investigator.
 
• Toxicity can be managed with a dose reduction following recovery to Grade 1 (or baseline) and optimal medical care.
 

a Elevations of aminotransferases when hepatic metastases are present may not require dose modifications if there is less than a doubling in the aminotransferases from baseline and if there are no progressive elevations in serum bilirubin concentration or coagulation factors.	

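### Section 7.9.13 lets a liver-injury hold end at a stable but ungraded level, Table 7.8 asks for Grade 1 or baseline, and no visible text says which sets the restart

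*Combined protocol and SAP*

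**What the plan says.** Section 7.9.13 has two triggers for a hold. One is related Grade 3 or higher hepatic injury, given as transaminases above 5 x ULN. The other is a transaminase rise accompanied by progressive bilirubin elevation and/or raised coagulation tests such as INR. After either, "cabozantinib should be interrupted until the etiology of the abnormalities is determined and these abnormalities are corrected or stabilize at clinically acceptable levels". The same paragraph adds: "Cabozantinib should be discontinued if hepatic dysfunction is not reversed despite interruption of study treatment".

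Table 7.8 gives grade-specific rules. For Grade 3: "Restart cabozantinib at a reduced dose after lab abnormalities have resolved to at least CTCAE Grade" 1 or lower, or baseline; and "Discontinue if lab abnormalities cannot be reversed despite interruption of study treatment". The Grade 2 row interrupts if the abnormality lasts longer than a week and restarts at the same threshold. The Grade 4 row discontinues unless there is clear, approved clinical benefit and the toxicity can be managed at a reduced dose after recovery to Grade 1 or baseline.

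Section 7.8.2 covers all toxicities. On recovery to Grade 1 or lower, or to baseline, if "the toxicity was deemed possibly related to study treatment, then study treatment may be restarted at a reduced dose".

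The liver-metastasis exception to dose modification appears twice. The text requires "no progressive changes in the aminotransferases (less than a doubling"); footnote a of Table 7.8 requires "less than a doubling in the aminotransferases from baseline".

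**The concern.** In the 7.9.13 sentence, stabilization is an alternative to correction, and what is acceptable is left to the site. Table 7.8 offers no such alternative. The two sit in one section and address the same Grade 3 event, so a site can find support for either action.

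At stake is re-exposure during drug-related liver injury that has not resolved, under a sentence that states no dose reduction. Section 12.1 plans up to 28 patients with liver metastases, Section 4.7 expects about eight sites, and Section 7.9.2 lists AST and ALT increases second and third among the laboratory adverse events. The visible laboratory eligibility criteria in Section 4.2 set no ALT or AST ceiling, so nothing there anchors the word acceptable.

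**Working it through.** There is no plan figure to reproduce. The check sets the rules side by side and then finds where they part.

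**Inputs (Table 7.8).** ALT/AST: Grade 1 up to 3.0 x ULN; Grade 2 above 3.0 to 5.0; Grade 3 above 5.0 to 20.0. Bilirubin: Grade 1 up to 1.5 x ULN; Grade 2 above 1.5 to 3.0.

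| Question | 7.9.13 text | Table 7.8 |
|---|---|---|
| When may a Grade 3 hold end? | Cause known, and corrected or stable at an acceptable level | Grade 1 or lower, or baseline |
| Dose at restart after Grade 3 | Not stated | Reduced |
| Stable Grade 2 | Not addressed | Interrupt if longer than 1 week |
| When to discontinue | Not reversed | Cannot be reversed |

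Neither column says whether a stable Grade 2 value counts as not reversed.

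**Where they part, on ALT/AST.**
- Above 5.0 x ULN they agree, because the text's own hold trigger still applies.
- At or below 3.0 x ULN, or at or below baseline, the table's threshold is met too.
- Between these, above 3.0 and up to 5.0 x ULN and above baseline, the text can release the hold and the table cannot. The band is 5.0 - 3.0 = 2.0 x ULN wide.

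By the same logic, bilirubin that is stable above 1.5 and up to 3.0 x ULN, and above baseline, is open to both readings. The visible table has no coagulation row, so there is no conflict on INR.

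**Worked case (assumed values).** Baseline is 1.0 x ULN, bilirubin normal, cause known. ALT rises to 8 x ULN (Grade 3), drug is held, and ALT settles at 4 x ULN (Grade 2).
- Text: the hold may end if the site judges 4 x ULN acceptable and does not call it unreversed.
- Table: no restart. If dosing did resume, the Grade 2 row would call for interruption once the elevation had lasted over a week.
- Section 7.8.1: a hold of more than 6 weeks for a related event leads to discontinuation unless benefit is unequivocal.

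**Does the liver-metastasis exception settle it?** It concerns whether a dose modification is needed, not when to restart. Even if borrowed for restart, its limit is 2 x baseline. In the case above, 4.0 / 1.0 = 4-fold, outside the limit. The limit covers none of the band at a baseline of 3.0 / 2 = 1.5 x ULN or less, and all of it only above 5.0 / 2 = 2.5 x ULN.

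**Is precedence stated?** Section 7.8.1 sends the reader to Section 7.9 for specific events, and 7.9.13 holds both versions. The note to Table 7.3 points to a Section 7.7.1, a heading that does not appear. Footnote b, which marks the Grade 2, 3 and 4 rows, is not visible.

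**The case against.** The strongest reply is that both rules can be followed. The text states a principle and gives no restart instruction; the table that follows gives the grades. A site that reads them together would apply the stricter one. This is a reasonable reading and it stands, but nothing visible requires it.

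Second, the sentence also ends holds for raised coagulation tests, which the visible table does not grade. A clinical-judgment standard therefore has a purpose there. This stands, and it limits the fix.

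Third, discretion appears intended: "Evaluation of subjects with elevated transaminases or bilirubin should be individualized". That sentence concerns evaluation, not the restart threshold.

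Fourth, Grade 2 is tolerated elsewhere. Section 7.10 discontinues patients who do not recover to tolerable Grade 2 or lower within 6 weeks, and Table 7.3 continues treatment through tolerable Grade 2 events. Neither is a restart rule for liver injury, but together they make it too strong to call 7.9.13 the only departure. Section 7.8.2 is also permissive, so it supports the table only by implication.

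Fifth, other limits remain: the cause must be known, unreversed dysfunction ends treatment, and drug-induced liver injury under Hy's Law means permanent discontinuation.

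A reader might infer that the two rules cannot both be obeyed, that the protocol certainly lacks a ranking, or that many of the 28 liver-metastasis patients are exposed. The documents support none of these. The stricter rule meets both, footnote b cannot be ruled out as settling the order, and no rate of Grade 3 injury or of Grade 2 plateau is given.

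**Conclusion.** The point holds as a narrow inconsistency in safety conduct. It lies in the restart threshold and dose after a hepatic hold, and it matters for stable ALT/AST above 3.0 and up to 5.0 x ULN and above baseline, with a parallel question for Grade 2 bilirubin. The number of patients cannot be derived from the documents. It should be small, because a patient must be held under 7.9.13 and then plateau in that range. The conclusion assumes that footnote b does not already rank the text and the table.

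A reader might also infer that Table 7.8 should simply override Section 7.9.13. It should not: the bilirubin and coagulation hold trigger and the Hy's Law discontinuation appear only in the text. No endpoint definition, sample size or error rate is affected. It is a change worth making because it is cheap and guards against re-exposure during unresolved injury.

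**What to change.** In Section 7.9.13, keep the requirement that the cause be determined and replace the rest of that condition with: *ALT, AST and bilirubin have resolved to Grade 1 or lower or to baseline, and any coagulation abnormality has resolved to baseline or a clinically acceptable level; restart, dose and Grade 4 handling per Table 7.8.*

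State that Table 7.8 governs the restart threshold and dose only. Say expressly that these remain in force:
- the hold trigger for transaminase rises with progressive bilirubin and/or INR elevation;
- permanent discontinuation under Hy's Law;
- the liver-metastasis exception, worded in both places as less than a doubling from baseline.

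If footnote b already sets the order, a cross-reference from the text to it would do.

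The cost is a wording amendment, less site discretion, and somewhat more time off drug for a few patients. Some of them could then reach the 6-week limit in Section 7.8.1, which keeps its exception for unequivocal benefit.
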